### 2.3. STUDY DESIGN SCHEMATIC

All subjects enrolled in the study will be followed for 30 days (+/- 5 day window) after completion of the study treatment. Subjects removed from study for unacceptable adverse events will be followed until resolution or stabilization of the adverse event.

## **2.5. SAFETY MONITORING**

Prior studies suggested that hypotension and methemoglobinemia may occur with the use of sodium nitrite. The study treatment of inhaled nitrite will be used safely with careful monitoring and prompt discontinuation of the study treatment in response to systemic hypotension with definitions of dose limiting toxicity as outlined in Table 1.

All subjects will be studied in UPMC Presbyterian Hospital Catheterization Laboratory with an investigator and nurse present at all times, and with continuous monitoring of vital signs and oxygen saturation. Subjects will also be monitored closely for methemoglobin levels during the study treatment.

Following study drug treatment, subjects will be evaluated as an outpatient at the clinic on Day 30 (+/- 5 day window). In addition, an interval telephone assessment will occur on Day 3. Subjects will be followed for evidence of acute or delayed adverse effects from the study treatment and to assess their clinical status. All adverse events experienced by subjects will be collected from the time of dosing, through the study and until the final study visit. Subjects continuing to experience toxicity at the off study visit may be contacted for additional assessments until the toxicity has resolved or is deemed irreversible. If possible, symptoms should be managed symptomatically. In the case of toxicity, appropriate medical treatment should be used.

In addition to these formal evaluations, subjects will be encouraged to immediately contact the study investigator and/or the study coordinator with questions, concerns, or to report new symptoms that occur during their study participation. If appropriate, based upon the evaluation, medical treatments will be provided to subjects, including appropriate referral to physicians or other services at the UPMC.

## **2.6. STOPPING RULES**

In addition to the dose limiting toxicity as outlined in Table 1 above, study treatment will be discontinued if any of the following occurs:

- A decrease in systolic BP > 40 mm Hg drop from pre-dose baseline;
- Desaturation > 10% from baseline;
- A single occurrence of venous methemoglobin level >5%;
- Severe DLT criteria met and symptomatic or requiring fluids or treatment;
- Any serious adverse event thought to be possibly related to the study treatment.

## **2.7. DRUG SUPPLIES**

### **2.7.1. Formulation and Packaging**

Formulation:

The active ingredient of the Sodium Nitrite Inhalation Solution (AIR001 Inhalation Solution) is sodium nitrite in a phosphate-buffered, pH adjusted solution for nebulization. The Sodium Nitrite Inhalation Solution is intended to be prepared prior to inhalational delivery to patients via electronic nebulization.

**Packaging:**

All vial formulations are labeled, packaged and distributed by Aires Pharmaceuticals, Inc. Aires Pharmaceuticals, Inc. will provide drug supplies to the investigational site.

**2.7.2. Availability**

AIR001 is an investigational drug and will be obtained from Aires Pharmaceuticals, Inc, San Diego, California. AIR001 will be supplied free-of-charge to investigators under a Collaborative Agreement between Aires Pharmaceuticals, Inc. and the University of Pittsburgh.

**2.7.3. Preparing and Dispensing**

The study drug will only be diluted and dispensed by the research pharmacist to the required dose concentrations.

The drug product will be delivered to subjects utilizing a nebulizer system supplied by Aires that is portable, highly efficient and that utilizes continuously vibrating mesh aerosol generation technology that allows a high percentage respirable dose delivery, minimal loss of drug to the environment between inhalations, and a reproducible droplet size distribution for optimal delivery of drugs to the distal pulmonary tree.

**2.7.4. Drug Administration**

The route of administration is by nebulization. It is anticipated that each nebulization will take approximately 10 – 15 minutes to deliver the dose. All doses specified in the protocol are the amounts of AIR001 placed into the nebulizer cup.

**2.8 DRUG STORAGE**

The investigational drug will be kept in its original packaging and stored in a locked, secure area at controlled room temperature (20 – 25° C) with the investigation drug services (IDS). The temperature of the storage area must be monitored to ensure compliance with required temperatures. A temperature log will be maintained to make certain that the drug supplies are stored at the correct temperature at all times maintained by IDS. Access to and administration of the investigational drug will be limited to the study investigators and authorized research staff. Study drugs may only be dispensed to subjects enrolled in this study.

**2.9. DRUG ACCOUNTABILITY**

The study investigators or the study coordinator will document the amount of study drugs dispensed and/or administered to subjects. The study drugs accountability records will be maintained throughout the course of the clinical trial by IDS. Any discrepancies in drug supplies will be noted and explained.

**2.10 STUDY PROCEDURES**

**2.10.1. Screening**

Screening evaluations to determine eligibility will take place prior to receiving study treatment. The potential study subjects are followed on a routine basis in the UPMC Heart and Vascular (HVI), Comprehensive Lung Center (CLC) or an inpatient at UPMC Presbyterian and are well known or referred to the study investigators. During routine clinical visit, patients who express interest in participation will undergo the screening assessment to determine that all inclusion/exclusion criteria are met prior to receiving the study treatment.

If the patient has had any of the tests done within the 6 months prior to the screening period, they will not be repeated for study purposes. The results collected from these tests and procedure will serve as a baseline for comparison of the subject's overall condition following study treatment. This visit may take up to 2 hours to complete.

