### **2.2 STUDY DESIGN AND METHODS**

#### **2.2.1. Study Design**

A total of 50 subjects with a confirmed diagnosis of pulmonary hypertension and meeting all inclusion/exclusion criteria will be enrolled in the study which will entail a single right heart catheterization. The study population consisted of subjects with WHO group I PAH (n=20), WHO group II (n=20) and subjects with WHO group III PH (n=10) will receive the following dose escalation paradigm: Each subject will receive a starting dose of 45 mg inhaled nitrite

(AIR001 Inhalation Solution), with one subsequent planned dose escalation of 90 mg inhaled nitrite, based on pulmonary vascular resistance response and safety and tolerability.

Screening (Day 0):

The potential study subjects are followed on a routine basis in the UPMC Heart and Vascular Institute (HVI), Comprehensive Lung Center (CLC) or an inpatient at UPMC Presbyterian, are well known or referred to the study investigator. Initial screening evaluations including physical examination, medical history, and clinical laboratory assessments will be conducted to determine study eligibilities during a routine clinic visit at the UPMC HVI, CLC or inpatient at UPMC Presbyterian. Subjects who meet the inclusion criteria and none of the exclusion criteria will be entered into the study.

Experimental Procedures (Day 1):

The study visit will occur on the same day subjects are scheduled for their clinically indicated right heart catheterization or who volunteer for a research right heart catheterization for this specific study. Subjects on oral background PAH therapy (ETRA or PDE5I) will be instructed to hold their regimen on the day of the study visit.

Subjects will be evaluated for additional medical history, physical examination, vital signs and pulse oximetry since screening. Laboratory testing will be repeated if baseline laboratory values are clinically significant and warrant repeat testing or inadvertently not collected at the screen visit. An echocardiogram with documentation of TRV for estimation of right ventricular systolic pressure and assessment of LV systolic and diastolic function will be performed pre and post nitrite inhalation.

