#### Pre-Dose: Baseline

- Physical examination to include vital signs, blood pressure, weight and oxygen saturation
- Laboratory testing that clinically warrants repeating testing or inadvertently not collected for screening may be obtained prior to research procedures
- Echocardiogram
- Non-invasive blood pressure measurement
- Right Heart Catheterization (RHC)-RA, RV, PA, pulmonary capillary wedge pressure (PCWP), CO/CI
- Inhaled NO testing at 40 ppm if PCWP < 25 with hemodynamic response recorded (RA, PA, PCWP, CO/CI)
- Micromanometry to record high fidelity pressure signals with simultaneous flow velocity from transthoracic echocardiographic ultrasound for the measurement of pulmonary arterial input impedance. Micromanometer pressure catheter is inserted via the Swann-Ganz catheter distal port.
- Repeat 2nd baseline hemodynamic measurement: RA, RV, PA, PCWP. CO/CI
- Pre-dose baseline PK, cGMP and platelet mitochondrial samples
- Pre-dose methemoglobin measurement

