## 2.11. SCHEDULE OF ACTIVITIES (STUDY ASSESSMENT TABLE)

The table below summarizes the protocol procedures that will be performed at screening, during the study treatment, and at follow-up.

Study Phase	Screening	Pre-Treatment	Treatment				Post-Treatment Follow-Up Monitoring	
Visit Type	Outpatient Clinic	Outpatient Cath Lab				Phone Assessment	Outpatient Clinic	
Days on Intervention	Day 0	Day 1				Day 3	Day 30	
Study Procedures		Baseline	Dose 1	Dose 2	Final Measurement			
Informed Consent	X							
Medical History and Demographics	X							
I/E Criteria	X							
Physical Exam	X	X					X	
Vital Signs	X	X					X	
Oxygen Saturation	X	X	X	X	X		X	
Laboratory Tests***	X	X					X	
Urine Pregnancy Test Δ	X	X						
Non-invasive blood pressure measurement		X	X	X				
Right Heart Catheterization (RHC): RA, RV, PA, PCWP, CO/CI (RV measurements at baseline, pre-dose and 60minute interval post last dose AIR001)		X	X	X	X			
Micromanometry		X			X			
Echocardiogram		X			X			
Inhaled NO at 40 ppm if PCWP < 25		X						
PK Sampling*		X	X	X				
metHgb Level§		X	X	X	X			
Plasma cGMP		X	X	X				
Platelet Mitochondrial Analysis		X	X	X				
AE Assessment	X	X	X	X	X	X	X	
Interval History Assessment						X		

Δ Urine pregnancy test will be performed only on female of childbearing potential.

\*\*\* Clinical laboratory tests may be repeated on study visit 1 if screen lab results deemed clinically significant and warrant repeat testing or inadvertently not collected at screen visit.

\* PK Sampling for Nitrite: Blood samples will be obtained at pre-dose and at the end of nebulization at the presumed peak nitrite concentration for each tolerated dosage time points; 15 minutes post inhalation.

§ Methemoglobin (metHgb) levels: will be measured at the following time points: pre-dose, 5, 15, 30 and 60 minutes each dose of AIR001 and at 120 minutes post last dose of AIR001.

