#### **2.12.6. Laboratory Testing**

Peripheral blood samples will be evaluated for baseline and follow-up comparison purposes which include complete blood count with differential, platelets, electrolytes, glucose, BUN, serum creatinine, liver function tests, PT/PTT, and nt-ProBNP. Urine pregnancy test may be performed only on female of child-bearing potential on Day 0 and Day 1.

Screening lab samples may be collected and analyzed at UPMC laboratories or at outlying facility of subject's choice. Lab results will be added to research chart for comparison. All 30-day samples will be analyzed at UPMC Presbyterian laboratory with the exception of the ntPro-BNP which may be processed and analyzed through the Pulmonary, Allergy and Critical Care Medicine (PACCM) research lab.

Baseline laboratory results within 6 months of screen visit may be used as baseline comparison and will not be repeated for research purposes. Blood samples may be collected on study visit 1 if baseline screening results are deemed clinically significant and warrant repeat testing or inadvertently not collected at screen visit.

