### **3.3 EXCLUSION CRITERIA**

Subjects meeting any of the exclusion criteria at baseline will be excluded from participating in study.

- Age less than 18 years;
- Baseline systemic hypotension, defined as MAP less than 50 mmHg;
- Required intravenous inotropes within 30 days prior to study participation;
- Has uncontrolled systemic hypertension as evidenced by sitting systolic blood pressure >160 mm Hg or sitting diastolic blood pressure >100 mm Hg at Screening;
- Has a history of portal hypertension or chronic liver disease, including hepatitis B and/or hepatitis C (with evidence of recent infection and/or active virus replication) defined as moderate to severe hepatic impairment (Child-Pugh Class B-C);
- Has chronic renal insufficiency as defined by serum creatinine >2.5 mg/dL at Screening or requires dialytic support;
- Has a hemoglobin concentration <9 g/dL at Screening;
- History of atrial septostomy within 6 months prior to Day 1 visit;
- Repaired or unrepaired congenital heart disease (CHD);
- Pericardial constriction;
- Confirmed diagnosis of restrictive or constrictive cardiomyopathy;
- Left ventricular ejection fraction <40% by multiple gated acquisition scan (MUGA), angiography or echocardiography;
- Symptomatic coronary disease with demonstrable ischemia;
- Other severe acute or chronic medical or laboratory abnormality that may increase the risk associated with study participation or investigational product administration or may interfere with the interpretation of study results and, in the judgment of the investigator, would make the subject inappropriate for entry into this study;
- Has a psychiatric, addictive or other disorder that compromises the ability to give informed consent for participating in this study. This includes subjects with a recent history of abusing alcohol or illicit drugs 30 days prior to study screening Day 0 and for the duration of the study;

- Poorly controlled asthma defined by active wheezing and/or cough with FEV1 < 70% predicted, responsive to inhaled BD (>15% increase in FEV1 with BD);
- Investigators, study staff or their immediate families;
- Clinically significant intercurrent illness (including lower respiratory tract infection) or clinically significant surgery within 4 weeks before the administration of study drug;
- Personal or family history of congenital or acquired methemoglobinemia;
- Personal or family history of RBC CYP B5 reductase deficiency;

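### Laboratory values up to six months older than screening can, by inference, settle the hemoglobin and creatinine exclusions, and no measured recheck is guaranteed before dosing

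*Combined protocol and SAP*

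**What the plan says.** Section 2.10.1 describes screening as the step that establishes eligibility. It then says that tests done "within the 6 months prior to the screening period, they will not be repeated for study purposes", and that the existing results will serve as a baseline for comparison. Section 2.12.6 says the same of the laboratory panel: "Baseline laboratory results within 6 months of screen visit may be used as baseline comparison and will not be repeated for research purposes". The screening panel listed in section 2.10.1 includes a complete blood count and serum creatinine.

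Two exclusions in section 3.3 rest on that panel: "Has a hemoglobin concentration <9 g/dL at Screening" and "Has chronic renal insufficiency as defined by serum creatinine >2.5 mg/dL at Screening or requires dialytic support". The synopsis times both the same way. The opening sentence of section 3.3 speaks of meeting a criterion at baseline.

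Day 1 testing is conditional. Section 2.2.1 says "Laboratory testing will be repeated if baseline laboratory values are clinically significant and warrant repeat testing" and adds tests not collected at screening. The pre-dose list in section 2.10.2 is permissive: "Laboratory testing that clinically warrants repeating testing or inadvertently not collected for screening may be obtained prior to research procedures". The footnote that qualifies the Day 1 laboratory mark in the section 2.11 schedule is also permissive: "Clinical laboratory tests may be repeated on study visit 1 if screen lab results deemed clinically significant and warrant repeat testing". No section states a maximum interval between screening (Day 0) and Day 1.

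**The concern.** An exclusion threshold protects a patient only if the value compared with it reflects that patient's present state. Here the value may predate screening by up to six months, and dosing by longer. A patient whose hemoglobin has since fallen below 9 g/dL, or whose creatinine has since risen above 2.5 mg/dL, could receive nitrite without anyone having a measurement that shows it.

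The sponsor set these limits, and section 5.2 lists the exclusion criteria first among the protections against study-drug risk. Section 1.3.5 explains that methemoglobin cannot bind oxygen, so a hemoglobin limit has a clear purpose with this drug. The protocol treats pregnancy differently: section 3.3 times that exclusion before dosing, and the schedule marks the test on both Day 0 and Day 1.

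**Working it through.** No statistical formula applies. The check sets the provisions side by side and follows one patient through them.

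**Step 1: age of the deciding value.** Let *g* be the interval from screening to Day 1.

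- Maximum age at screening = 6 months (sections 2.10.1 and 2.12.6), which is 181 to 184 calendar days.
- Maximum age at dosing = 6 months + *g*.
- *g* has no stated limit, so the age at dosing has no stated limit either. With *g* = 0 it is 6 months.

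**Step 2: what prompts a Day 1 repeat.**

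| Section | Force | Trigger |
|---|---|---|
| 2.2.1 | *will* | earlier value clinically significant and warranting a repeat, or not collected |
| 2.10.2, pre-dose list | *may* | clinically warranted, or not collected |
| 2.11, footnote | *may* | screening result clinically significant and warranting a repeat, or not collected |
| 2.12.6 | *may* | as in 2.11 |

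The only mandatory statement, in section 2.2.1, looks back at the earlier value. The wording in section 2.10.2 might cover a reason that first appears on Day 1, but it leaves the test optional.

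**Step 3: four cases for hemoglobin (creatinine is parallel).**

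1. No earlier value: the catch-up provision applies and a sample can be drawn.
2. Earlier value beyond the limit: the patient is excluded.
3. Earlier value acceptable but near the limit: it may well be judged clinically significant, and section 2.2.1 then calls for a repeat.
4. Earlier value unremarkable, present value beyond the limit: nothing about the earlier value prompts a repeat, and no section requires a new measurement.

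Case 4 is the gap.

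**Step 4: whether another provision requires a measurement.**

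- Day 1 history, examination, vital signs and pulse oximetry (section 2.2.1) measure neither quantity. Saturation and methemoglobin are percentages and do not show total hemoglobin.
- The exclusions for blood loss over 550 mL within 90 days, and for significant illness or surgery within 4 weeks, depend on a known event.
- The investigator-judgment exclusion ("Other severe acute or chronic medical or laboratory abnormality that may increase the risk associated with study participation") applies only to an abnormality that someone has found.
- The remark on hemoglobin evaluation in section 5.2 stands in the paragraph on blood-sampling volume and names no test or time.
- Sections 2.12.5 and 2.12.8 collect laboratory values as covariates. They name neither test and require no review before dosing.

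None of these requires a measured hemoglobin or creatinine before dosing.

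**The case against.** The strongest reply has three parts.

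First, neither section 2.10.1 nor section 2.12.6 says that old results decide eligibility; the stated use is baseline comparison. This is correct, and a reader who takes the protocol to state the eligibility use outright goes too far. It is an inference. It rests on the no-repeat rule standing directly after the sentence on confirming eligibility, and on the absence of any separate eligibility sample.

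Second, section 3.3 opens with criteria met at baseline, and section 2.10.2 limits treatment to patients who meet none of the exclusions. Eligibility is therefore not worded purely as of screening. But the protocol uses *baseline* both for the Day 1 pre-dose column and for the screening laboratory results, and section 2.10.1 makes reused results the baseline. The duty stands, but no new measurement follows from it.

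Third, the patients are clinic patients, inpatients or referrals, Group I patients on therapy must have been stable for 3 months, and the Day 1 checks would bring many changes to light. This stands as a reason why the risk is small. It also corrects a natural assumption that near-threshold patients are the most exposed. Their values are the most likely to prompt a repeat, so an unremarkable value that has since worsened is less well covered.

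It is also fair to say that nothing in the documents shows six months to be wrong for these two tests, or that any particular shorter limit is right.

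**Conclusion.** The point holds as a minor safety tightening. The plan allows a hemoglobin or creatinine value that is six months old at screening, and older without stated limit at dosing, to stand as the only value behind an exclusion. This assumes that reused results serve eligibility as well as comparison, and that sites follow the no-repeat rule as written. At most the 50 planned subjects are affected.

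The documents do not support stronger readings. They give no distribution of hemoglobin or creatinine and no rate of change, so neither the number of patients who would cross a limit nor a rate of harm can be estimated. A reader might also infer that an unrecognised low hemoglobin makes the drug's methemoglobin effect dangerous; the documents give no basis for sizing that. Nor do they settle whether old laboratory values could touch the PVR endpoint. Section 2.12.1 allows Fick cardiac output but does not say which hemoglobin value would enter it, so no claim is made either way.

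**What to change.** Keep the existing catch-up bullet in the section 2.10.2 pre-dose list, because it also covers other screening tests that were missed, such as PT/PTT and nt-ProBNP. Add a second bullet:

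*Hemoglobin and serum creatinine, from a clinical result obtained within 30 days before Day 1 or from a sample drawn on Day 1 after consent, will be reviewed against the section 3.3 exclusions before catheterization.*

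The 30 days are an example; the sponsor should set the limit. Bring sections 2.2.1, 2.10.1 and 2.12.6 and the section 2.11 footnote into line, which also removes the conflict between *will* and *may*. Change the timing of the two exclusions in section 3.3 and the synopsis to match. Drawing the sample after consent fits section 2.10.1, which allows consent on Day 1, and section 4.2, which requires consent before any research procedure.

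The cost is about one routine panel for each subject without a recent result: about 50 at most, plus any for patients who fail screening that day. There would be a short wait for results and an occasional same-day screen failure in someone already present for catheterization. No extra visit is needed, and the schedule already has a Day 1 laboratory column.
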